	

• POSAS (PI Assessment) – Abdominoplasty 5 cm Segments (Part B and Part B Extension)

• POSAS (Subject Assessment) – Abdominoplasty 5 cm Segments (Part B and Part B Extension)

• Independent Panel Review of scar photography using POSAS

• Excision site histology

• Tensile strength of scar

 
Exploratory
 

• POSAS (Subject Assessment) – Excisions (Part A)

Safety Evaluations	

• Adverse Events (Part A and Part B)

• Treatment Related Adverse Events (Part B Extension)

• Clinical safety laboratory tests

• Immunogenicity

Sample Size	Approximately 25 subjects will be enrolled. This is a Phase I safety/proof-of-concept + Phase IIa study and a formal sample size justification is not required. It is the opinion of the Sponsor that a total of 25 subjects will be sufficient to achieve the objectives of the study.
Statistical Methods	All statistical processing will be performed using SAS® version 9.4 or later unless otherwise stated. Statistical significance will be based on two-tailed tests of the null hypothesis resulting in p-values of 0.05 or less. For categorical parameters, the number and percentage of subjects or observations in each category will be presented. The denominator for percentage will be based on the number of subjects or observations appropriate for the purpose of analysis. For continuous parameters, descriptive statistics will include n (number of subjects or observations), mean, standard deviation, median, and range. Comparisons between treatment groups will be performed using parametric or non-parametric testing, as appropriate. Statistical analyses will be conducted on an intent-to-treat (ITT) basis. An interim analysis will be conducted when all subjects have completed Study Part A.

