### 10.2 Assessments of Efficacy

Efficacy analyses will be conducted on an intent-to-treat (ITT) basis (see Section 10.4).

For categorical parameters, the number and percentage of subjects/observations in each category will be presented. The denominator will be based on the number of subjects/observations appropriate for the purpose of analysis. For continuous parameters, descriptive statistics will include n (number of subjects or observations), mean, standard deviation, median, and range.

Comparisons between treatment groups will be performed using parametric or non-parametric testing, as appropriate.

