### 10.3 Assessment of Safety

For Parts A and B, safety analysis will be conducted on the Safety Population (SAFT), by tabulations of AEs, safety laboratory parameters and immunogenicity outcomes.

Subjects will be followed for AEs (local and systemic) throughout the study. Events specific to treatment sites will be recorded by excision site (Study Part A) and per side (Study Part B) to allow comparison of study treatments.

For Part B Extension, Safety analysis will be conducted on the ITT population. Subjects will be followed for Treatment-Related AEs (local and systemic) throughout the study.

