#### 10.3.1 Adverse Events

All AEs occurring during the study will be recorded and classified on the basis of MedDRA terminology. Descriptions of AEs will include the date of onset, the date the AE ended, the severity of the AE, the relationship to study medication, the action taken regarding study medication usage, the action taken to treat the AE, and the outcome. All reported treatment-emergent AEs (TEAEs) will be summarized by the number of Subjects reporting AEs, system organ class, severity, seriousness, and relationship to study medication. TEAEs are those AEs with an onset on or after the date of initial IP exposure.

AEs will be summarized by treatment group and severity, and by treatment group and relationship to IP. Each subject will be counted only once within a system organ class or a preferred term by using the AEs with the greatest relationship within each category.

All information pertaining to AEs noted during the study will be listed by subject, detailing verbatim given by the PI, preferred term, system organ class, start date, stop date, severity, actions taken, and drug relatedness.

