## **10.4 Analysis Populations**

### **10.4.1 Primary Population for Efficacy Analysis**

The ITT population will be the primary population for efficacy and safety analyses and will consist of all randomized subjects who received at least one injection of IP and provided at least one post-baseline evaluation, and will be analyzed in the treatment group they were allocated.

A per-protocol (PP) population will neither be identified nor analyzed.

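### Protocol 10.4.1 names ITT for safety where 10.3 and 10.4.2 use the safety population, and the once-per-subject AE rule in 10.3.1 is not limited to the relationship table

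*Protocol*

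**What the plan says.** **Populations.** Protocol Section 10.3 assigns safety populations by study part. It states "For Parts A and B, safety analysis will be conducted on the Safety Population (SAFT"), and it uses ITT for safety in the Part B Extension. Section 10.4.2 assigns SAFT to safety with no limit by part; SAFT needs one injection of product and is analysed by treatment received. Section 10.4.1, whose heading refers to efficacy only, states: "The ITT population will be the primary population for efficacy and safety analyses and will consist of all randomized subjects". Members must have been injected and must have "provided at least one post-baseline evaluation, and will be analyzed in the treatment group they were allocated". The Synopsis (Statistical Methods) says "Statistical analyses will be conducted on an intent-to-treat (ITT) basis", whereas Section 10.2 limits the same statement: "Efficacy analyses will be conducted on an intent-to-treat (ITT) basis".

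**Counting rule.** Section 10.3.1 says that treatment-emergent AEs will be "summarized by the number of Subjects reporting AEs, system organ class, severity, seriousness, and relationship to study medication". It then names two tables: "AEs will be summarized by treatment group and severity, and by treatment group and relationship to IP". The next sentence gives the only once-per-subject rule in the protocol: each subject is "counted only once within a system organ class or a preferred term by using the AEs with the greatest relationship within each category".

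**The concern.** Safety and tolerability is the primary objective of Parts A and B, and this is a first-in-human trial. The safety population and the AE summary tables are therefore part of the main analysis of those parts.

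On populations, two sections give different answers to the same question. The sets differ both in who is included and in the treatment to which an event is attributed. Each subject receives both treatments, one on each side, so attribution means attribution to a side.

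On counting, a rule that selects a subject's AE by its relationship to the product suits a relationship table. In a severity table it can select an event that is not the subject's worst. The design makes several AEs per subject under one term plausible: Part A has 6 to 9 sites per treatment in each subject, Section 10.3 records treatment-site events by excision site, and Section 9.6.3.2 reports independent events separately.

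**Working it through.** The plan gives no figure to reproduce here, so the check sets the passages side by side.

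**Step 1: which population each section names for safety**

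| Section | Parts A and B | Part B Extension |
|---|---|---|
| 10.3 | SAFT | ITT |
| 10.4.1 | ITT (no limit by part) | ITT |
| 10.4.2 | SAFT | SAFT (no limit by part) |
| Synopsis | ITT (general sentence, safety not named) | ITT (same sentence) |

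For Parts A and B, 10.4.1 contradicts 10.3 and 10.4.2. For the Extension, 10.4.2 contradicts 10.3 and 10.4.1. Only 10.3 distinguishes the parts explicitly.

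**Step 2: when the choice changes a result**

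- *Membership.* A subject who is injected but has no post-baseline evaluation is in SAFT and not in ITT. This group may be empty. Section 9.2.2 schedules an AE assessment and post-excision photography at Visit 2a, the injection day, and 10.4.1 does not say whether these count as a post-baseline evaluation.
- *Attribution.* If the left and right syringes are exchanged, an AE at a treated site or side goes to the allocated treatment under ITT and to the treatment received under SAFT. Events that are not specific to a side are unaffected.

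In every other case the two sets give the same tables.

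**Step 3: the counting rule applied to the severity table**

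Section 9.6.3.4 has three severity grades and Section 9.6.3.5 two relationship levels. Take one subject with two AEs under the same preferred term:

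| AE 1 | AE 2 | Greatest relationship selects | Severity shown | Maximum severity |
|---|---|---|---|---|
| Mild, Related | Severe, Not Related | AE 1 | Mild | Severe |
| Severe, Related | Mild, Not Related | AE 1 | Severe | Severe |

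The first row is the problem: a milder Related event displaces a more severe Not Related one. The second row shows that the rule does no harm when the Related event is at least as severe.

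**Step 4: does another section supply a severity rule?**

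Section 9.6.3.4 assigns each AE the maximum severity that it reached. That rule works within one AE. It does not say which of several AEs represents the subject, so it does not correct the first row.

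**Step 5: what remains visible**

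Section 10.3.1 lists every AE by subject with its severity and relatedness, and it includes seriousness among the summaries. The displaced event disappears from one table only. In the Extension only treatment-related AEs are recorded, so the pairing in the first row cannot arise among events recorded there.

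**The case against.** **The counting sentence plainly means the relationship table.** It follows directly on the mention of that table, and this is probably the intent. The text does not say so, however: the preceding sentence names both tables and no other rule is given for severity. What stands of this objection is that the defect is one of wording and may never reach a programmed table.

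**Table conventions belong in the SAP.** Section 10 defers the analyses to a separate SAP, which was not available here. This disposes of one tempting extension: that the protocol fails because it does not say which AE to count when two have the same relationship but different severity. That is ordinary SAP detail and no fault in the protocol. It does not dispose of a rule that the protocol states without restriction, or of two sections that name different populations.

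**10.3 is the more specific text and settles the population.** It is more specific, and the heading of 10.4.1 suggests that its reference to safety is a slip or was meant for the Extension. The contradiction is still on the page.

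**The Synopsis sentence is weak evidence.** This is accepted. It follows a remark on comparing treatment groups and does not name safety. A reader might infer that it deliberately moves all safety analysis to ITT; the documents do not support that, since 10.3 says otherwise in detail.

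**Stronger readings.** A reader might also infer that severe events would be lost from the report, or that injected subjects would be dropped from the safety analysis. Neither is supported. The listings keep all events, and the same-day assessments at Visit 2a may leave no injected subject outside ITT.

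**Conclusion.** The text is wrong as written on both points, and the matter is minor.

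The population conflict between 10.4.1 on one side and 10.3 and 10.4.2 on the other is direct for Parts A and B. The smaller conflict between 10.4.2 and 10.3 over the Extension is also direct. Its effect depends on a subject without a post-baseline evaluation or on a side swap. The protocol gives no expected rate for either, so no number is attached.

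The counting rule can understate a subject's severity only if it is applied to the severity table, and only where a more severe Not Related AE sits beside a milder Related one under the same term. How often this would happen cannot be derived from the protocol. The effect is confined to summary tables. Neither point affects the data collected, the efficacy analysis or the by-subject listings. The conclusion rests on the protocol alone; a SAP may already handle the tables correctly, but the protocol passages would still need to agree.

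**What to change.** 1. **10.4.1:** limit the reference to safety to the Part B Extension.
2. **10.4.2:** limit SAFT to safety in Parts A and B. Together with the first change, this makes 10.4 match 10.3 and leaves the ITT choice for the Extension as it is. Deleting the safety reference from 10.4.1 alone would not be enough, because 10.4.2 would still conflict with 10.3 for the Extension.
3. **Synopsis, Statistical Methods:** restrict the ITT sentence to efficacy analyses, as 10.2 does.
4. **10.3.1:** replace the counting sentence with: *In severity tables each subject is counted once per SOC/PT at maximum severity; in relationship tables, once per SOC/PT at greatest relationship.*

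The cost is a few words in four places, with no new data and no change to study conduct. The one downside for the sponsor is that the severity table may look slightly less favourable.

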### **10.3.2 Safety Laboratory Tests**

Determination of clinical significance for all out-of-range laboratory values will be made by each PI, and Adverse Event reports will be generated as necessary.

### **10.3.3 Immunogenicity**

Changes from baseline in immunogenicity outcomes will be summarized with descriptive statistics and text, as appropriate.

### **10.3.4 Concomitant Medications**

All previous therapies and concomitant medications will be classified based on terminology from the WHO Drug Dictionary. Previous therapies and concomitant medications data will be presented in data listings.

No concomitant medication will be recorded in the eCRF for Part B Extension.

## **10.4 Analysis Populations**

### **10.4.1 Primary Population for Efficacy Analysis**

The ITT population will be the primary population for efficacy and safety analyses and will consist of all randomized subjects who received at least one injection of IP and provided at least one post-baseline evaluation, and will be analyzed in the treatment group they were allocated.

A per-protocol (PP) population will neither be identified nor analyzed.

### **10.4.2 Populations for Safety Analysis**

The SAFT population will be used for safety analysis and will consist of all randomized subjects who received one injection of IP, and will be analyzed as per the treatment actually received.

### **10.4.3 Sub-Populations**

A subset of subjects with a history of keloidal scarring will be analyzed for efficacy and safety in a separate report. Comparisons between this subject population and the general population will not be made.

## **10.5 Subject Disposition**

A tabulation of subject disposition will be provided which will include the numbers of subjects who enter, complete, and discontinue the study. The reasons for discontinuation will be included.

## **10.6 Protocol Deviations and Violations**

All protocol deviations and violations will be reported to the Sponsor and recorded throughout the study. A tabulation of protocol deviations will be included in the final study report.

## **10.7 Multicenter Issues**

The study will be conducted at multiple investigational centers in the United States with the intention of pooling the results for analysis.

## **10.8 Missing Efficacy Data Imputations**

Data will be analyzed as observed; no imputations will be made for missing data.

## **10.9 Statistical Hypothesis Testing and Control of Multiplicity**

Not Applicable.

## **10.10 Compliance**

No compliance analyses are planned.

## **10.11 Interim Analyses**

An interim analysis will be performed utilizing data from study Part A.

## 11 QUALITY CONTROL AND QUALITY ASSURANCE

### 11.1 Study Monitoring

An initiation visit will be conducted with the PI/OP, IDR and study coordinator(s) by Sponsor and/or its designee. During this meeting, an extensive review and discussion of the protocol, all study procedures, source documents, and eCRFs will be conducted. Evaluation scales will be reviewed extensively.

The study monitors/clinical research associates will be trained prior to study initiation. Following this training, an overview of the study disease and study material background will be understood. Specific monitoring guidelines and procedures to be followed during monitoring visits will also be utilized. For Parts A and B, all data will be approximately 100% source document verified by the site monitors. All subject source records must be made available to the monitors.

For Part B Extension, sites will be monitored remotely. On-site monitoring will not be conducted.

The conduct of the study will be closely monitored by the Sponsor (or designate) following GCP guidelines. The reports of these verifications will also be archived with the study report. In addition, inspections or on-site audits may be carried out by local and/or federal authorities. The PIs will allow the Sponsor's representatives and any regulatory agency to examine all study records, corresponding subject medical records, clinical dispensing records and storage area, and any other documents considered source documentation. The PIs agree to assist the representative, if required.

### 11.2 Audits and Inspections

The study will be conducted under the Sponsorship of the Sponsor in conformation with all appropriate local and federal regulations, as well as ICH guidelines. Interim and end-of-study audits of raw data, study files, and final report may be conducted by the Sponsor's Quality Assurance Department or designee.

The Sponsor is responsible for implementing and maintaining quality assurance and quality control systems to ensure that studies are conducted and data are generated, documented, and reported in compliance with the protocol, GCP, and applicable regulatory requirements. In addition, the Sponsor will be responsible for securing agreement from all involved parties to ensure direct access to all study related investigational centers, source data/documents, CRFs, and reports for the purpose of monitoring and auditing by the Sponsor, and inspection by regulatory authorities.

### 11.3 Protocol Deviations

The PIs must read the protocol thoroughly and must follow the instructions exactly.

A deviation from the protocol is an unintended and/or unanticipated departure from the procedures and/or processes approved by the Sponsor and the IRB and agreed to by the PI. Deviations usually have an impact on individual patients or a small group of patients and do not involve inclusion/exclusion or primary endpoint criteria.

A protocol violation occurs when there is non-adherence to the protocol that results in a significant, additional risk to the patient, when the patient or PI has failed to adhere to significant protocol requirements (inclusion/exclusion criteria) and the patient was enrolled without prior Sponsor approval, or when there is non-adherence to FDA regulations and/or ICH GCP guideline.

The issue of noncompliance may be either on the part of the subject, the PI, or the study site staff. As a result of deviations, corrective actions are to be developed by the site and implemented promptly.

It is the responsibility of the site to use continuous vigilance to identify and promptly report deviations to ethica CRO Inc.

All protocol deviations and violations must be addressed in study subject source documents. A completed copy of the ethica CRO Inc. Protocol Deviation Form must be maintained in the regulatory file, as well as in the subject's source document. Protocol deviations must be sent to the IRB per its guidelines.

The protocol must be rigorously adhered to; however, exceptions will be made in emergency situations when the protection, safety, and well-being of the subject requires immediate intervention based on the judgment of the PI.

## **12 ETHICS AND ADMINISTRATIVE ISSUES**

### **12.1 Ethical Conduct of the Study**

This study will be conducted in accordance with the ethical principles originating from the Declaration of Helsinki, ICH guidelines, GCP, and in compliance with local regulatory requirements. The PI agrees, when signing the protocol, to adhere to the instructions and procedures described in it and thereby to adhere to the principles of GCP.

### **12.2 Ethics Review**

This protocol, proposed informed consent form and other information to subjects, and all appropriate amendments will be reviewed and approved by an Institutional Review Board (IRB). A signed and dated notification of the IRB approval will be provided to the Sponsor and PI prior to study initiation. The name and occupation of the chairman and members of the IRB will be supplied to the Sponsor to the extent allowable by the IRB. The PI will provide required progress reports and report all SAEs to the IRB as required by the IRB.

### **12.3 Written Informed Consent**

This study will be conducted in compliance with 21 CFR Part 50 for informed consent.

Written informed consent will be obtained from each subject before any procedures or assessments are done and after the aims, methods, anticipated benefits, potential hazards, compensation and/or honoraria, and insurance arrangements are in force. It will also be explained to the subject that they are free to refuse entry into the study and free to withdraw from the study at any time without prejudice to future treatment.

The site will keep the original consent forms and copies will be given to the subjects.

### **12.4 Subject Data Protections**

Subject data will be protected by ensuring that no captured data contain subject names, addresses, telephone numbers, email addresses, or other personally identifying information. It is acknowledged that subject initials, demographics (including birthdates), medical histories, and prior concomitant medication uses, along with the name and address of the enrolling PI may allow for personal identification of study participants. Other than where necessary to meet regulatory requirements, all data collected in this study will be presented in tabulated (i.e., aggregate) form and listings containing information that could be used to identify an individual subject will not be included in any public disclosures of the study data or the study results.

### **12.5 Data Monitoring Committee**

Not applicable.

### **12.6 Financial Disclosure**

Financial disclosures will be obtained from Investigators and Co-Investigators to document any potential conflicts of interest.

### **12.7 Investigator Obligation**

The PI agrees, when signing the protocol, to adhere to the instructions and procedures described in it and thereby to adhere to the principles of Good Clinical Practice (GCP).

### **12.8 Changes to the Protocol**

The PIs must read the protocol thoroughly and must follow the instructions exactly. Whenever

possible, any planned deviations should be agreed to by prior discussion between the Sponsor and the PI, with appropriate documentation of Sponsor approval prior to effecting the changes agreed upon. Any amendment to the protocol containing major modifications (particularly if it may involve an increased risk to the subjects) will be approved by the IRB before it may be implemented. No change in the conduct of the study can be instituted without written approval from the Sponsor.

### **12.9 Confidentiality Regarding Study Subjects**

All the data furnished to the PI and his/her staff and all data obtained through this protocol will be regarded as confidential and proprietary in nature and will not be disclosed to any third party, except for the FDA or other regulatory body, without written consent from the Sponsor.

